4.1. Design

The proposed study is a randomized control pilot trial of at least 60 and up to 70 women newly diagnosed with early-stage breast cancer who are finishing primary treatment. Participants will be randomized either to the intervention arm (CCC website that will provide information on team-based follow-up care for both cancer surveillance and preventive care) or the control arm (static online survivorship care plan template which was adapted from the ASCO breast cancer survivorship template). The feasibility and acceptability of the tool and correlations with patient-reported outcomes will be assessed 3 months following the completion of the baseline survey. A sample of 8-10 patients in the intervention arm will then be invited to participate in debriefing interviews to collect feedback regarding their experience with the CCC tool. We will also ask for feedback from 4-6 providers (2-3 medical oncologists and 2-3 PCP's) whose patients participated in the study. Due to time and budget constraints, we are only able to include a sample of patients and providers in our debriefing interviews.

4.2. Subject Recruitment

Since this pilot study is testing a behavioral intervention and not a therapeutic intervention, the following outlines our standard approach to recruitment and enrollment of subjects, which have been successfully used in prior studies of UM breast cancer patients. For subject recruitment,

we will follow the approach used previously by [name] in her iCanDecide recruitment (HUM 62261). The iCanDecide Study was a two-armed randomized controlled trial of an interactive and tailored website with the goal of helping newly diagnosed and early stage breast cancer patients make informed treatment decisions. Employing the same recruitment strategy as used in the pilot study for iCanDecide, a trained clinical research associate will recruit a sample of at least 60 and up to 70 women from the University of Michigan Breast Cancer Clinic who are completing primary treatment for early-stage breast cancer, ages 21-84, and finishing their active treatment visits with their medical oncologist. A study coordinator will identify eligible patients for the pilot testing by reviewing MiChart scheduled oncology visits for patients nearing the end of their treatment and reports from the breast oncology meetings. Patients' eligibility for participation in the study will be verified with the UM breast oncology care team and the PI. Once an eligible patient is identified as being at the end of their primary treatment, the study coordinator will identify their next scheduled visit with medical oncology and plan to be there in person to initiate recruitment. At that visit, the study will be introduced to the patient by the attending oncologist, and those who are interested in participating will then meet with the study coordinator to discuss the following packet of materials: (1) a cover letter written at a 6th grade reading level containing instructions, information about the study including the risks and benefits, their rights as participants and that participation is voluntary; (2) log-in information to access the website which contains the informed consent for them to complete; (3) a copy of the informed consent which they will complete online; (4) information about how to receive a \$20.00 electronic Amazon gift card once subjects have completed the online baseline questionnaire, (5) a local telephone number to call with questions or concerns, and (6) an additional \$20 Amazon gift card included in the study packet to encourage enrollment of participants. For patients' convenience, the study coordinator will provide patients' with the option to view the CCC website or access it via a laptop computer or ipad. When a patient logs into the website, she will be asked to verify personal information and complete the informed consent. The PI and study coordinator(s) will verify subjects' enrollment into the study via their online completion of the consent form and baseline questionnaire, as indicated on the CCC Administrative Dashboard.

This process will request contact information, including providing an address and telephone number to support following up after the follow-up survey has been emailed to participants if needed, sending the electronic gift card to participants via email, and contacting those interested in participating in debriefing interviews at the completion of the study.

Inclusion Criteria:

1. Ability to voluntarily provide written IRB-approved informed consent and communicate satisfactorily with the investigator, to participate fully in the study, and comply with all its requirements.
2. Women diagnosed with Stages 0-II breast cancer
3. Women who are currently receiving care from a breast oncologist at UMCCC
4. Women who are completing their primary treatment for breast cancer and transitioning into survivorship
5. Access and ability to use the Internet

Exclusion Criteria:

1. Women who are unable to speak and/or read English

4.3. Subject Selection

After completion of the baseline questionnaire, participants will be randomized to either enter the *ConnectedCancerCare* website (n=30-35), or a static website (n=30-35) which contains a brief survivorship care plan template in PDF format (see Appendix). We will employ block randomization, with a block size of 6 (10-12 blocks total) to ensure that the study group assignments are equally distributed throughout recruitment.

[figure not shown]
[figure not shown]

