Objectives	
Aim 1: To conduct a pilot evaluation to assess the feasibility and acceptability of a patient-centered, web-based navigation tool, ConnectedCancerCare, that supports the transition from breast cancer treatment to survivorship and promotes team-based survivorship care.
 
Aim 1A: To assess the feasibility of recruiting at least 60 and up to 70 women with early-stage breast cancer who are completing primary treatment in the breast oncology clinic to the study.
 
Aim 2A: To assess the acceptability of the CCC website among the 30 women randomized to the CCC intervention group.
 
Aim 2: To explore whether CCC influences patient and provider communication about team-based survivorship care, patient-reported knowledge about team-based survivorship care and follow-up visit scheduling in primary care.
 
Aim 3: To conduct debriefing interviews with participating patients and providers in the intervention group to inform the future evaluation and implementation of the tool.

Study Design	Pilot randomized control trial
Eligibility Criteria	
1. Ability to voluntarily provide written IRB-approved informed consent and communicate satisfactorily with the investigator, to participate fully in the study, and comply with all its requirements.2. Women diagnosed with Stages 0-II breast cancer

	3. Women who are receiving care from a medical oncologist 4. Women who are completing their primary treatment for breast cancer and transitioning into survivorship
Statistical Considerations	As this is a pilot study, we will be primarily assessing whether the recruitment of at least 60 and up to 70 women is feasible, and whether the majority of participants (50%) report the tool is acceptable using descriptive statistics. We will assess differences in patient-reported outcomes between the intervention group and control group, but this is an exploratory analysis to guide future versions of the tool and our planned multi-site RCT. As such, a sample size of at least 60 women and up to 70 participants is sufficient to address our primary outcomes (see power calculation section).
Number of Participants	At least 60 and up to 70 women (30-35 intervention and 30-35 control arm)
Estimated Enrollment Period	9 months
Estimated Study Duration	12 months

1. Objectives/Specific Aims

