4.4.2. Provider Summary: The results of the baseline questionnaire will populate a short patient summary and highlight any critical misconceptions, or expectations the patient has about her care and who will be managing it, any gaps in knowledge she has about follow-up care, and a short checklist for her to use to guide her continuing care. Providers of patients randomized to the CCC intervention website will receive a summary based upon patients' answers to the baseline questionnaire for the six areas outlined in the Provider Summary. They include: 1) patient diagnosis and treatment; 2) knowledge of follow-up care; 3) preferences for follow-up care from PCP vs. Oncologist; 4) hormone therapy requirement; 5) personal health concerns; and 6) level of recurrence worry. Providers of patients in the control group will not receive a summary report for these patients.

Figure 5. Provider Summary for Follow-Up Care	
Patient Information Provided	
Diagnosis and Treatment Summary	
Knowledge about Follow-Up Care	
	
 • Questions about diagnosis • Follow-Up services needed
Preferences for Oncologist vs. PCP	
Hormone Therapy (Yes/No)	
	
 • Adherence • Side effects
Personal Concerns	
	
 • Top 3 concerns
Recurrence Worry	

4.4.3. Follow-up Questionnaire: At three months, patients in both groups (intervention and control) will be emailed and prompted to complete a brief, online survey by logging back into the CCC website. The survey includes multiple measures of acceptability and usability in the intervention group only (primary outcomes) as they relate to viewing the tool (described in detail in section 5 below). Also, we will explore the influence of the intervention on secondary patient-reported outcomes including whether they scheduled a visit with their PCP and their knowledge about continuing (survivorship) care, as outlined in section 5 below.

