4.5. Time and Events Table

Study Events	Pre-study (after completing primary treatment)	Time 1 (When viewing the website initially)	Time 2 3 months post-baseline questionnaire completion)	Time 3 1-3 months post-follow-up questionnaire completion)
Informed Consent	X			
Baseline Questionnaire	X			
Randomization		X		
View intervention or control website		X		
Follow-up questionnaire			X	
Debriefing Interviews				X

5. Measures

The measures described in detail below were selected after literature review, and were directly informed by our conceptual model and the results of our prior work and pilot data. The measures are described by specific aim below:

Aim 1A: Feasibility

Feasibility will be defined by the successful recruitment of at least 60 women with half randomized to the intervention website and half to the control website over a 9-month time period. Based upon positive response rates of patients in previous studies of survivorship interventions and the iCanDecide pilot trial, we anticipate approaching approximately 87 women in order to achieve a similar response rate of 80% enrollment (n=70). We will also assess the proportion of those successfully recruited who complete the baseline survey and the follow-up survey. In addition, we will capture paradata including participants' average number of page views, and average time on website.

Aim 1B: Acceptability

Acceptability and usability will be defined by asking participants in the intervention arm to rate their experiences with the tool on 5 point Likert-type scales, as follows: (1) CCC was easy to use, (2) CCC was helpful during my transition to survivorship, (3) CCC helped me think about when to see my PCP and when to see my oncologist, (4) I would recommend CCC to other patients, (5) The time it took to go through the website (6) The amount of info.

Based on our prior work, we will use a cut off of 50% of more reporting a score above 3 as acceptable within that domain. We will also examine the distributions within each domain and determine how we can make the next versions of the tool more acceptable to patients as needed. We will then create a summary score of acceptability by averaging the responses to the 6 items, with a score of 3 or more indicating the tool was acceptable to the majority of patients.

Aim 2: Exploratory patient-reported outcomes

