Patient Recruitment for Pilot Testing Patients will be recruited through the Breast Cancer Clinic at the University of Michigan Rogel Cancer Center. Patients eligible for the pilot testing will be those who have recently finished their primary treatment for newly-diagnosed stage I-II female breast cancer and have scheduled their transition visit with the medical oncologist. For the pilot, we will recruit English speaking women with internet access.

Patient and Physician Recruitment for Debriefing Interviews: As stated in section 4.4, a convenience sample of 8-10 patients who participated in the intervention arm and answered that they were willing to be contacted for additional information regarding their experience with using the website on the follow-up survey will be invited to participate in debriefing interviews. We will contact these participants via email and invite them to participate in the debriefing interviews about the usefulness of the tool and future implementation strategies. Debriefing interviews will also be held with 4-6 of their physicians (2-3 medical oncologists and 2-3 primary care physicians) to obtain their views on the usefulness and usage of the tool by their patients and future enhancements.

Sources of Materials: All data to be used in this project will come from: 1) electronic patient surveys (pilot testing), 2) MiChart patient records (participant eligibility), and 3) patient and provider interviews. Survey data will include baseline data collected through the navigation tool, and then follow-up survey data for participants in the intervention three months later. Digital audio recordings will be taken during each physician and patient debriefing interview to be transcribed and analyzed.

8.1. Adequacy of Protection Against Risks: We use established human subjects' protection protocols that address the limited use of personal health information, transfer of de-identified datasets within our institution, storage of information from various data sources and surveillance and response to adverse events. The primary risks of the study are related to breaches in confidentiality and patient concerns about the use of their medical information. We have a long track record of employing the highest standards of patient confidentiality. However, we will respond promptly to any patients or providers who contact the staff or investigators about any concerns related to the study.

9. Data Safety and Monitoring

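### A single fixed block size of 6 at one clinic, with no allocation concealment described, could let anyone recruiting who learns past assignments foresee some allocations: a minor risk to Aim 2, cheaply removed

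*Combined protocol and SAP*

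**What the plan says.** **Allocation.** Section 4.3: "We will employ block randomization, with a block size of 6 (10-12 blocks total". No other block size and no stratification factor appears. Section 5 (Aim 1A) sets equal arms: "with half randomized to the intervention website and half to the control website over a 9-month time period". The Study Summary gives the sample size: "At least 60 and up to 70 women (30-35 intervention and 30-35 control arm".

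**Timing.** Section 4.3: "After completion of the baseline questionnaire, participants will be randomized to either enter the" tool website or the static control site. Section 4.4.4 lets the coordinator telephone a woman up to twice within 14 days if her baseline questionnaire is unfinished.

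**Setting and recruiters.** Section 8: "Patients will be recruited through the Breast Cancer Clinic at the University of Michigan Rogel Cancer Center". In section 4.2, candidates come from oncology schedules and breast oncology meeting reports, and eligibility is verified with the care team and the investigator. Then "the study coordinator will identify their next scheduled visit with medical oncology and plan to be there in person to initiate recruitment". The treating physician raises the study with the woman before the coordinator meets her. The coordinator can offer a laptop or iPad, and enrolment is verified on an administrative dashboard.

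**Routes by which the arm may become known.** Under section 4.4.1 the research coordinator verifies the physician contact details used for faxing a summary. Section 4.4.2 adds: "Providers of patients in the control group will not receive a summary report for these patients".

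**Analysis.** Section 7 compares the arms on the Aim 2 outcomes with chi-square and t-tests, without adjustment. The Study Summary calls this comparison exploratory and says it is to guide the planned multi-site trial.

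The text does not say how the sequence is generated, who can see assignments, or whether the dashboard shows the arm.

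**The concern.** When every block has the same size and that size is written in the protocol, a person who knows the earlier assignments can count down each block. Once one arm has its three places, the rest of the block is determined. One clinic without strata means one sequence to follow.

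Randomising after consent and baseline prevents anyone from acting on an assignment already made. It does not prevent anticipation of the next one. Some discretion comes before allocation: how warmly the study is introduced, how persistently an unfinished baseline is pursued, and the exclusion in section 8 that a surgeon may apply for clinical or nonclinical reasons.

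Aim 2 is the only comparison between randomised arms. If more engaged women tended to enter one arm, the differences in knowledge, communication and primary care scheduling would partly reflect who was recruited. Those differences are meant to inform the later trial.

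**Working it through.** **Inputs.** Block size 6 and 10-12 blocks (section 4.3); equal allocation, so 3 + 3 per block (section 5, Aim 1A); total 60-70 (Study Summary); one clinic (section 8).

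**1. The plan's own figure.** 60/6 = 10 and 70/6 = 11.67, which rounds up to 12. The stated 10-12 blocks is reproduced.

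**2. Certain allocations in one block.** There are C(6,3) = 20 equally likely blocks. An allocation is certain once one arm is full.

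- Positions 1-3: 0.
- Position 4: the first three are all in one arm, 2 × 1/20 = 0.10.
- Position 5: three of the first four are in one arm, 2 × C(4,3)/20 = 8/20 = 0.40.
- Position 6: 1.00.

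Sum = 1.5 of 6 = 25%. The closed form 2m/(m+1) with m = 3 gives 6/4 = 1.5, which agrees.

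**3. Over the trial.**

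- 60 women: 10 × 1.5 = 15 (25%).
- 70 women: 11 full blocks give 16.5, and the four women of the last block add 0.10, so 16.6 (23.7%).
- 18 is reached only if all 12 blocks, 72 women, are filled.

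**4. Effect of women still pending.** The 25% assumes that the woman approached is the next one randomised. If k consented women will be randomised before her, the recruiter sees k fewer assignments.

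- k = 1: certainty is possible only at position 5 (0.10) and position 6 (0.40), so 0.50/6 = 8.3%.
- k = 2: only at position 6 (0.10), so 0.10/6 = 1.7%.
- k = 3: 0%.

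As a guide, assume even accrual over 9 months (about 39 weeks). Then 60-70 women is 3.1 to 3.6 enrolments per 14 days. Some women pending is therefore plausible, but so is completion at the same visit. The documents do not settle which is usual.

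**5. Guessing without certainty.** Always guessing the arm with more places left gives an expected m + 2^(2m-1)/C(2m,m) - 1/2 correct per block. With m = 3 this is 3 + 32/20 - 0.5 = 4.1 of 6 = 68.3%, against 50% by chance.

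**6. Varied blocks.** These results are simulated for 66 allocations, with an observer who knows the set of sizes but not the size of each block.

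| Scheme | Certain in advance | Best guess correct |
|---|---|---|
| Fixed 6 | 25% | 68.3% |
| Random 4, 6 | 5.5% | 69.1% |
| Random 4, 6, 8 | 2.3% | 67.9% |

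Varying the size removes nearly all certainty but hardly changes better-than-chance guessing. Only keeping past assignments from the recruiter removes that.

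**The case against.** The strongest reply is that the route to bias is inferred. Section 4.2 uses the dashboard to confirm consent and baseline completion, not to show the arm. Section 4.4.1 describes contact verification for patients generally and does not say who sends the fax. If the website allocates silently and recruiters never see the result, blocks of 6 do little harm. This stands: the text neither shows that assignments are visible to recruiters nor says that they are hidden.

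A reader might also infer that the coordinator freely chooses whom to approach and when. Section 4.2 does not support that. Approach is tied to the next scheduled oncology visit, eligibility is checked with others, and the oncologist introduces the study. What remains is discretion over effort and follow-up.

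A third inference would be that any steering could be neither seen nor corrected. The baseline questionnaire (section 4.4.1) is completed before randomisation. It records knowledge, primary care provider status, provider preferences, satisfaction with coordination, communication and worry about recurrence. Imbalance on these can be checked and adjusted for. The reply is only partial, because the planned tests are unadjusted and engagement as such is not among the listed measures.

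Finally, Aim 2 is exploratory. The recruitment count does not depend on the arm, and acceptability involves no comparison between arms. That lowers the priority, but it is not a reason to keep a predictable sequence when a better one is cheap.

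**Conclusion.** The point holds as a minor, inexpensive improvement. Section 4.3 specifies a predictable scheme, and the text describes nothing that keeps assignments from those who recruit. The ceiling is 25% of allocations certain in advance (15 of 60, about 17 of 70). It falls to 8.3% with one woman pending and 1.7% with two.

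The ceiling rests on three assumptions: all past assignments are known, they are known in order, and the woman approached is the next one randomised. The documents establish none of them.

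A reader might conclude that a quarter of allocations will be known, or that Aim 2 is biased. The documents support neither. No steering, motive or effect on an outcome is shown, and no size of bias can be calculated from them. What exists is a risk to one exploratory comparison. This conclusion concerns the written text only; the figures that follow section 4.3 were not legible in the copy read.

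**What to change.** In section 4.3:

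1. State that the website generates the sequence in randomly varied permuted blocks, for example of 4, 6 and 8, and allocates automatically once the baseline questionnaire is complete.
2. State that block sizes and sequence are withheld from anyone who approaches or reminds patients, and take the sizes out of the protocol copy those staff use.
3. Remove the arm from the dashboard view used for recruitment and baseline reminders, and say who sends the provider summaries. Oncologists will still be able to infer the arm of their own patients from those summaries, which is a further reason to vary the block sizes.

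Item 1 without items 2 and 3 leaves best-guess accuracy near 68%, so the parts belong together.

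**Cost.** A small programming or view-setting change; the documents do not describe how either is built, so the effort should be confirmed with the developers. Final balance may be slightly worse. With blocks of at most 8, the arms can differ by at most 4, for example 37 and 33 at 70, or 32 and 28 at 60. The present scheme is exactly balanced at 60 but not guaranteed at 70: after 11 full blocks the last four women split 2:2 or 3:1, giving 35/35 or 36/34.

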4.4. Intervention (*ConnectedCancerCare*)

Overview: The CCC tool is a personalized, navigation website that is tailored to patients' preferences for provider roles in follow-up care, their satisfaction with their current PCP, and their worry about cancer recurrence. This pilot study is designed to determine whether an informative and tailored website can assist in guiding patients to utilize team-based care for their follow-up cancer care. The tool involves a website and text-based reminder system to help patients transition from active cancer treatment to ongoing/survivorship, team-based care and includes three research phases: 1) baseline survey and 2) 3-month follow-up survey among all participants; and 3) patient/provider interviews among a sample of participants in the intervention arm to assess patients' understanding of survivorship care, usage of the website, and increased knowledge of team-based survivorship care as a result of using the tool. This tool was developed by the UM Center for Health Communications Research (CHCR) under the direction of the PI, [name], with input from oncologists, primary care physicians and other study co-investigators, and then beta tested among breast cancer patients. We believe this tool will be of benefit to patients comfortable using the internet and to clinicians who value additional information about their patients' preferences and concerns.

Development: CCC was developed using "agile development",⁴³⁻⁴⁵ which included content development and usability testing as used previously by the investigators in a trial of a patient decision aid for breast cancer treatment.²⁶ CCC was developed using an iterative, agile cycle, which included planning (content decisions), design (graphical display and media elements), development (programming) and testing (feedback from stakeholders on draft versions). Testing included an iterative process of tailoring, timing, data, and functionality. The next phase (Phase 2) includes the pilot evaluation detailed in this protocol (Figure 3).

Content: The content of the CCC navigation tool was developed by Drs. [name] and [name], along with clinical experts in the UM-RCC and CHCR. The development built upon the existing programming of the iCanDecide tool, a novel treatment decision-making tool developed by [name], which recently was evaluated in a full-scale randomized control trial with 500 patients (REF). CCC includes content focused on four areas as outlined in the conceptual model:

- 1) **Inform:** This section provides the patient with key facts about survivorship guidelines and what to expect from team-based care.

- 2) **Clarify:** This section provides tailored content to clarify appropriate provider roles in delivering team-based care based on their collected preferences. The preferences outlined in the questionnaire section are used to tailor the content on this page.
- 3) **Communicate:** This section promotes communication with the oncologist and PCP about this topic and includes tips and suggestions on how to communicate with their physicians and get the most out of their clinic visits.
- 4) **To do list for follow-up care and reminders:** This sections outlines for patients what services they will need during survivorship, based on clinical guidelines. Customized alerts will be sent to participants to remind them to schedule their follow-up visits with their PCP, according to the guideline-recommended schedule and to complete their follow-up survey. A total of three reminders for each event have been built into the website program, and subjects are given the choice of how they want to receive reminders (i.e. text or email). Currently, the ConnectedCancerCare website is not linked to MiChart; however, that is a desired feature for future development.

Screen shots of the website content and information on how to access the website directly are included in Appendices 5.

4.4.1. Baseline Questionnaire: After completing the online consent, patients will begin the online questionnaire which collects information that is used to tailor the content of the website. The survey is included in the Appendix. Measures used to tailor the website content include the following:

- a. Knowledge of guidelines for breast cancer follow-up screening and preventive care
- b. Current PCP (yes/no)
- c. Preferences for providers in team-based (PCP or oncologist)
- d. Satisfaction with care coordination at the time of transition
- e. Communication with providers about continuing care
- f. Worry about recurrence

We will also ask patients to provide the contact information for their medical oncologist and primary care physician as part of the baseline questionnaire, which will be used to fax a provider summary to both physicians' offices. The research coordinator will then verify this contact information using MiChart and the internet (for address verification) as needed.

4.4.2. Provider Summary: The results of the baseline questionnaire will populate a short patient summary and highlight any critical misconceptions, or expectations the patient has about her care and who will be managing it, any gaps in knowledge she has about follow-up care, and a short checklist for her to use to guide her continuing care. Providers of patients randomized to the CCC intervention website will receive a summary based upon patients' answers to the baseline questionnaire for the six areas outlined in the Provider Summary. They include: 1) patient diagnosis and treatment; 2) knowledge of follow-up care; 3) preferences for follow-up care from PCP vs. Oncologist; 4) hormone therapy requirement; 5) personal health concerns; and 6) level of recurrence worry. Providers of patients in the control group will not receive a summary report for these patients.

Figure 5. Provider Summary for Follow-Up Care	
Patient Information Provided	
Diagnosis and Treatment Summary	
Knowledge about Follow-Up Care	
	
 • Questions about diagnosis • Follow-Up services needed
Preferences for Oncologist vs. PCP	
Hormone Therapy (Yes/No)	
	
 • Adherence • Side effects
Personal Concerns	
	
 • Top 3 concerns
Recurrence Worry	

4.4.3. Follow-up Questionnaire: At three months, patients in both groups (intervention and control) will be emailed and prompted to complete a brief, online survey by logging back into the CCC website. The survey includes multiple measures of acceptability and usability in the intervention group only (primary outcomes) as they relate to viewing the tool (described in detail in section 5 below). Also, we will explore the influence of the intervention on secondary patient-reported outcomes including whether they scheduled a visit with their PCP and their knowledge about continuing (survivorship) care, as outlined in section 5 below.

4.4.4. Patient Contacts: If a patient decides to participate, they will log into the CCC website using the unique assigned ID access code provided with the recruitment letter. Upon initial login, they will consent online, create their account (by inputting their email and phone number) and begin the baseline survey. They will receive one automated email reminder 2 days later if the baseline questionnaire is not completed, and up to 2 personalized phone contacts from the study coordinator within 14 days if the baseline questionnaire remains uncompleted. Upon completion of the baseline questionnaire, participants randomized to the intervention arm will receive weekly reminders via email, and possibly text messages if they opted into texting at account creation to make an appointment with their PCP. Three months from baseline completion, participants will receive a 1-week advance alert email (and a text if they opted in) for the follow-up questionnaire, followed by a second email alert in the next week, indicating the survey's availability on the CCC website. Participants will receive one automated email reminder 5 days later if the follow-up questionnaire is not completed. We will employ a modified version of the Dillman method, which includes up to 3 contacts for follow-up to maximize response rates and to identify non-respondents, that has proven to be successful in our previous work.

4.4.5. Debriefing Interviews: A sample of 8-10 patients who participated in the pilot testing and 4-6 of their physicians (2-3 medical oncologists and 2-3 primary care physicians) will be contacted via phone and invited to participate in debriefing interviews about the usefulness of the tool and future implementation strategies. A question will be included at the end of the follow-up survey which solicits their interest in being contacted after the study ends to discuss their experience with *ConnectedCancerCare* in more detail. For those who respond yes, we will select the first 8-10 people and contact them via phone to conduct a brief 20-minute audiotaped, interview (questions are in the Appendix), to gather their feedback about their experience with the tool.

